7.9. Final Study Visit

The final study visit should be done at 5 years (+/- 60 days) following the PulseRider procedure. A DSA or MRA will be performed and all other post-procedure assessments will be completed. Any ongoing AE/SAEs should be reviewed, assessed for resolution and any documentation completed. Upon exit from the study, the subject will undergo standard follow-up with their doctor and data will not be collected.

7.10. Unscheduled Visit

Subjects returning for an unscheduled visit indicating new or unresolved signs and/or symptoms will be documented as an unscheduled follow-up and, at the investigator's discretion, be reported as an adverse event. Information to be collected, at a minimum includes:

- Neurological exam
- National Institutes of Health Stroke Scale – NIHSS
- Review of relevant medications
- Review of adverse events

This is provided in the Schedule of Assessments. Radiographic imaging is completed at the discretion of the investigator based upon the subject's condition and standard of care. If performed, the imaging should be sent to the core lab.

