7.6. Follow-up in the Event of Stroke or Suspected Stroke

If a subject experiences a stroke, or if there is any symptom or suspicion of a stroke, in addition to the hospital/physician routine standard of care for stroke, the following instructions apply:

1. Obtain Magnetic Resonance Imaging (MRI) or Computed Tomography (CT) if indicated within 24 hours after the onset of symptoms.
2. Contact the Sponsor about the event.
3. Complete the stroke specific AE form and perform the neurological exams, NIHSS and mRS.

In the event that the subject experiences a stroke but the investigator did not learn of the stroke at the time it occurred, and if a MRI was not done, the investigator should obtain a MRI as soon as possible upon learning of the stroke, and complete steps 2-3 above.

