8.1. Specific Safety Parameters

8.1.1. Adverse Event (AE)

An adverse event (AE) is defined as any untoward medical occurrence, unintended disease or injury, or untoward clinical signs (including abnormal laboratory findings) in subjects, users or other persons, whether or not related to the investigational medical device (ISO 14155:2011E).

- Note 1: This definition includes events related to the investigational medical device or the comparator
- Note 2: This definition includes events related to the procedures involved
- Note 3: For users or other persons, this definition is restricted to events related to the investigational medical devices

For the purposes of this protocol, adverse events will be reported and recorded (via eCRF) if any of the following apply:

- The event is neurological in nature
- The event is a serious adverse event
- Causality is related to:
 - the device
 - the procedure
 - dual antiplatelet medication
 - if causality is unknown

Any medical condition that is present at the time the participant is screened or prior to the start of the study procedure will be considered as baseline and not reported as an AE. Such conditions should be added to medical history, if not previously reported.

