8.5. Clinical Events Committee

The Clinical Events Committee (CEC) will consist of a minimum of three independent physicians with expertise in neurosurgery, neurology or interventional neuroradiology and who are not otherwise involved with the study. The CEC will review all reportable adverse events to adjudicate the safety endpoint, in addition to AEs of interest specified in the CEC charter.

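### Section 7.10 makes adverse event reporting discretionary at unscheduled visits, which conflicts with section 8.1.1 and leaves a narrow gap for neurological signs the investigator does not attribute to stroke

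*Combined protocol and SAP*

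**What the plan says.** Five parts of the protocol bear on this.

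- **Section 7.10 (Unscheduled Visit).** A return for signs or symptoms that are new or have not resolved is documented as an unscheduled follow-up. Whether it also becomes an adverse event (AE) is left to the investigator: it will, at the investigator's "discretion, be reported as an adverse event". The minimum data set for the visit includes a neurological examination, an AE review and the "National Institutes of Health Stroke Scale – NIHSS".
- **Section 8.1.1 (Adverse Event).** Reporting is mandatory: "adverse events will be reported and recorded (via eCRF) if any of the following apply". The first condition listed is "The event is neurological in nature". Serious events, and events related to the device, the procedure or dual antiplatelet medication, are listed as well.
- **Section 7.6 (Stroke or Suspected Stroke).** The trigger is broad: "If a subject experiences a stroke, or if there is any symptom or suspicion of a stroke". The site must then "Contact the Sponsor about the event" and "Complete the stroke specific AE form and perform the neurological exams, NIHSS and mRS". Nothing in this section is discretionary or tied to a type of visit.
- **Section 8.4.2.** All serious AEs go to the sponsor within 72 hours, whether or not they are related to the device or procedure.
- **Section 8.5, repeated in 10.4.** "The CEC will review all reportable adverse events to adjudicate the safety endpoint". The same sentence adds AEs of interest named in the CEC charter.

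**The concern.** Sections 7.10 and 8.1.1 give a site different answers to the same question. A subject returns between visits with a new neurological sign. Under 8.1.1 an AE of that kind must be reported; under 7.10 the investigator may choose. Section 7.10 contains no exception for neurological events, no cross-reference to 7.6 or 8.1.1, and no order of precedence.

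This matters because of where the choice sits. The primary safety endpoint (neurological death or major ipsilateral stroke up to 1 year) is adjudicated by an independent CEC, but the CEC works from events that sites have reported. In a single-arm trial the investigator making the choice knows the treatment and usually gave it. Whether a set of signs amounts to a major ipsilateral stroke is a question for the CEC, and it should not be settled before the CEC sees the case.

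The resulting error has one direction. Under section 10.3.4, a subject who completes 1 year without a recorded event counts as a success, so a missed event in a completer turns a failure into a success. In a subject who leaves early, it replaces a certain failure with an imputed value. Neither change can raise the subject's contribution to the event rate.

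**Working it through.** **Step 1. Which cases does the discretion in 7.10 actually reach?**

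| Situation at an unscheduled visit | Rule that applies | Does 7.10 leave a real choice? |
|---|---|---|
| Stroke recognised or suspected | 7.6: sponsor contact and stroke AE form; 8.1.1: neurological | No |
| Event meets the definition of serious | 8.1.1 and 8.4.2: report within 72 hours | No |
| New neurological signs, not serious, not thought to be stroke | 8.1.1 says report; 7.10 says discretion; 7.6 is not triggered | Yes, by direct conflict |
| Non-neurological symptom, not serious, unrelated | Not reportable under 8.1.1 | Yes, and harmlessly |

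Only the third row is exposed. It depends on the site's own judgement that the signs are not stroke and not serious.

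**Step 2. Would another stated route bring a third-row case to the CEC?** The NIHSS is recorded at the visit (7.10 and Table 7.15A), so a rise would be in the database. No section of the protocol sends an NIHSS rise to the CEC when no AE form exists. The CEC charter is not among the documents and may contain such a rule.

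**Step 3. How close to the decision limit could a single event matter?** This is an illustration only.

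Inputs: 160 subjects and 10% attrition (section 10.2), giving 160 × 0.90 = 144; success if the upper bound of a two-sided 95% normal-approximation interval is below 15% (10.1.1); anticipated rate 7% (10.2).

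Upper bound = p + 1.96 × √(p(1 − p)/n), with p = events/144:

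- 14 events: 0.0972 + 1.96 × √(0.0972 × 0.9028/144) = 14.56%, pass
- 15 events: 0.1042 + 1.96 × √(0.1042 × 0.8958/144) = 15.41%, fail
- 16 events: 0.1111 + 1.96 × √(0.1111 × 0.8889/144) = 16.24%, fail

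Each event is worth 1/144 = 0.69 percentage points. At the anticipated 7%, about 0.07 × 144 = 10.1 events are expected, some way inside the limit.

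**Step 4. What would under-reporting do at the boundary?** The miss rates are assumptions, because the documents state none. With a true rate of 15% and success at 14 or fewer of 144, the number of recorded events is binomial with probability 0.15 × (1 − fraction missed).

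| Assumed share of events missed | Recorded rate | Chance of passing |
|---|---|---|
| 0% | 15.0% | 4.3% |
| 5% | 14.25% | 7.0% |
| 10% | 13.5% | 11.1% |
| 20% | 12.0% | 24.3% |

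These figures show how sensitive any site-reported endpoint is to missed events. They do not measure the effect of section 7.10. The planned analysis also differs from this one: it uses the modified intent-to-treat set with multiple imputation (10.3.4).

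**The case against.** A reader might infer that 7.10 allows a stroke to bypass adjudication. The documents do not support that. Section 7.6 applies to any stroke and to any symptom or suspicion of one, at any time, and extends to strokes the investigator learns of late. A neurological death is a serious AE by definition, and a major stroke would usually meet the hospitalization or permanent-impairment criteria in 8.1.2, so 8.4.2 applies too. A stroke left unreported would breach the protocol; 7.10 does not license it.

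The defence has other good points:

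- The discretion has an ordinary purpose. Section 7.10 covers symptoms of every kind, including unresolved ones that may belong to an AE already on file.
- Back-up detection exists. Monitors verify source documents (section 9 and 10.4), and the subject's information card asks that the investigator be told of outside neurological evaluations (7.7.2).
- It would be wrong to say that the CEC sees nothing except reportable AEs, because 8.5 adds AEs of interest from a charter that cannot be examined here.

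All of this narrows the point without removing it. Section 7.6 starts from the site's suspicion. Where the site does not suspect stroke, 8.1.1 is the safeguard, and 7.10 is worded against it. A monitor who finds such a visit without an AE form could be shown 7.10 as permission.

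**Conclusion.** The conflict between 7.10 and 8.1.1 is real and should be removed. Its reach is limited to neurological signs that the treating investigator neither regards as serious nor attributes to stroke. For those, the protocol text gives no certain route to the CEC, and any resulting error favours meeting the 15% goal.

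The size cannot be estimated from the documents. One event can decide the result when the count lies at 14 or 15 of 144, but nothing shows that events would be missed, and the anticipated rate is well below that margin. A reader should not take the passing probabilities above as a forecast.

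The conclusion assumes that the CEC charter does not already require referral on an NIHSS change. If it does, what remains is a wording conflict. I rate the point as moderate: a cheap improvement, not a condition for the trial's validity.

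**What to change.** 1. Reword 7.10 so that the investigator's discretion does not extend to events reportable under 8.1.1 or covered by 7.6, and cross-refer to both. The 7.10 minimum assessments also omit the mRS, which 7.6 requires after a suspected stroke; the cross-reference would resolve that.

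2. Add a check in the electronic data capture system. Any NIHSS rise of 4 or more over the pre-procedure score, at any scheduled or unscheduled visit up to 1 year, goes to the CEC whether or not an AE form exists. This is a screen; the CEC still decides whether the endpoint definition is met. If the charter already contains such a rule, state it in the protocol.

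3. Reconcile the major-stroke threshold. The Protocol Summary sets it at a rise of at least 4, while section 3.2.1 sets it at more than 4 and defines minor stroke as a rise of 1 to 3, so a rise of exactly 4 falls in neither class there. A trigger at 4 or more captures cases under both definitions while this is settled.

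The cost is a sentence, a database query on data already collected, and a few more AE forms and CEC packets. No visit or treatment changes.

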7.11. Retreatment

At the discretion of the investigator, a subject who has received a PulseRider device may be retreated (e.g. with coils, stent, etc.) at any time. All subjects who are retreated will remain in the study and will continue to receive all follow-up assessments based on the date of the index procedure per the Schedule of Assessments in Section 7.15. When a subject returns for a retreatment, this is considered an unscheduled visit and the evaluations noted for unscheduled visits must be completed. Data from the retreatment procedure will be captured in the appropriate eCRF, and data from the remaining unscheduled assessments will also be captured in the eCRFs. No pre-planned staged procedures on target aneurysms will be allowed in the study.

7.12. Early Termination

The study can be discontinued at the discretion of the investigator or study Sponsor for reasons including, but not limited to, the following:

- Per recommendation of the Data Monitoring Committee (DMC)
- Unanticipated adverse device effect (UADE) presenting an unreasonable risk to subjects (Sponsor may terminate the study immediately)
- Obtaining new scientific knowledge that shows that the study is no longer valid or necessary
- Insufficient recruitment of subjects
- Persistent non-compliance of a site with the protocol, or IRB/regulatory requirements

If the study is discontinued or suspended prematurely at a single clinical site (e.g. due to non-compliance or lack of enrollment), the Sponsor shall inform the clinical investigator/investigational center of the termination or suspension in enrollment and the reason for this. The Sponsor will also inform site personnel that although enrollment will be halted, the currently enrolled subjects will continue to be followed per protocol through

the five-year follow-up visit and then exited from the study. The Sponsor's communication to the investigator/investigational center will also include instructions for the investigator to promptly inform the IRB regarding the change in study status, along with the reason for termination or suspension by the Sponsor. Regulatory authorities may also need to be informed if deemed necessary.

[figure not shown]
If the entire study is discontinued or suspended prematurely, the Sponsor shall promptly inform all clinical investigators/investigational centers of the termination or suspension in enrollment and the reason for this. The Sponsor will also inform site personnel that although enrollment will be halted, the currently enrolled subjects will continue to be followed per protocol until one year visit for safety. Once the subject has completed the one year follow-up visit for safety, they will be exited from the study. The Sponsor's communication to the investigators/investigational centers will also include instructions for the investigator or their delegated study staff to promptly inform all consented subjects at their center, as well as the IRB regarding the change in study status along with the reason for termination or suspension by the Sponsor or by the clinical investigator. The Sponsor will notify the FDA in writing of the action, per regulations. Regulatory authorities and the personal physicians of the subjects may also need to be informed if deemed necessary.

7.13. Lost to Follow-up

Every attempt will be made to have all subjects complete the follow-up visit schedule. A subject will not be considered lost to follow-up until the last study visit and unless efforts to obtain compliance are unsuccessful. At a minimum, the effort to obtain follow-up information will include three attempts to make contact via telephone/email and if unsuccessful, then a letter from the investigator, sent via FedEx or similar traceable method, will be sent to the subject's last known address. Both contact logs and letter contact efforts to obtain follow-up will be recorded in the subject study files.

7.14. Schematic of Study Design

Figure 7.14A Schematic of Study Design

7.15. Schedule of Assessments Table

This table provides an overview of the procedures to be performed at each study visit and the visit window.

Table 7.15A Schedule of Assessments

Assessments	Pre-procedure* (0-60 days of the procedure)	Immediately Pre-Procedure	Procedure	Immediately Post-procedure	Discharge	30 Day Follow-up (+/- 7 days)	180 Day Follow-up (+/-42 days)	1 Year Follow-up (+/-60 days)	2 Year Telephone Call (+/- 60 days)	3 Year Follow-up (+/-60 days)	4 Year Telephone Call (+/- 60 days)	5 Year Follow-up (+/-60 days)	Unscheduled Visit
Informed Consent	X												
Medical History	X												
Labs (CBC & Blood Coagulation Tests)	X												
Neurological Exam	X				X	X	X	X		X		X	X
NIH Stroke Scale Assessment		X			X	X	X	X		X		X	X
Modified Rankin Scale		X			X	X	X	X	X	X	X	X	
Pregnancy Test		X [*]											
Conventional Catheter Angiography – DSA [§]	**X	***X				O ^β	O ^β	X ^{†\$}	O ^β	X ^{††}	O ^β	X ^{††}	O ^β
MR Angiography [§]						O ^β	O ^β		O ^β	X ^{††}	O ^β	X ^{††}	O ^β
CT Angiography [§]	**X					O ^β	O ^β		O ^β		O ^β		O ^β
Review of Adverse Events			X	X	X	X	X	X	X	X	X	X	X
Review of Medications Taken	X		X	X	X	X	X	X	X	X	X	X	X
Medical Resource HECON		X	X	X	X	X	X	X	X	X	X	X	X

*With the exception of the baseline DSA or CTA and the pregnancy test, all baseline evaluations must be completed within 60 days prior to the index procedure and may occur on the procedure day prior to the procedure.

**Baseline imaging may be either CTA or DSA and must be completed within 180 days prior to the index procedure.

***Three treatment angiograms: 1) Immediately pre-procedure image is before PulseRider implant to confirm eligibility 2) Procedure image immediately after PulseRider placement 3) Immediately post-procedure is after coiling.

^β Any imaging related to the target aneurysm conducted post-procedure and prior to the final study visit, per standard of care, will be collected.

[†] Imaging for 1 year post-procedure must be DSA.

^{††} Imaging for 3 year 5 years post-procedure must be DSA or MRA.

[‡] Pregnancy test must be completed on day of procedure for women of childbearing potential.

[§] Subjects who were not implanted with the PulseRider device are not required to undergo DSA imaging at 1 year.

8. Assessment of Safety

8.1. Specific Safety Parameters

8.1.1. Adverse Event (AE)

An adverse event (AE) is defined as any untoward medical occurrence, unintended disease or injury, or untoward clinical signs (including abnormal laboratory findings) in subjects, users or other persons, whether or not related to the investigational medical device (ISO 14155:2011E).

- Note 1: This definition includes events related to the investigational medical device or the comparator
- Note 2: This definition includes events related to the procedures involved
- Note 3: For users or other persons, this definition is restricted to events related to the investigational medical devices

For the purposes of this protocol, adverse events will be reported and recorded (via eCRF) if any of the following apply:

- The event is neurological in nature
- The event is a serious adverse event
- Causality is related to:
 - the device
 - the procedure
 - dual antiplatelet medication
 - if causality is unknown

Any medical condition that is present at the time the participant is screened or prior to the start of the study procedure will be considered as baseline and not reported as an AE. Such conditions should be added to medical history, if not previously reported.

8.1.2. Serious Adverse Event (SAE)

A serious adverse event (SAE) is defined (ISO 14155:2011E) as an adverse event that:

- Led to death
- Led to serious deterioration in the health of the subject, that either resulted in
 - a life-threatening illness or injury, or
 - a permanent impairment of a body structure or a body function, or
 - in-patient or prolonged hospitalization, or

- medical or surgical intervention to prevent life-threatening illness or injury or permanent impairment to a body structure or a body function
- Led to fetal distress, fetal death or a congenital abnormality or birth defect

Note: Planned hospitalization for a pre-existing condition, or a procedure required by the clinical investigation plan, without serious deterioration in health, is not considered a serious adverse event.

8.1.3. Adverse Device Effect (ADE)

An adverse device effect is defined as an adverse event related to the use of an investigational medical device (ISO 14155:2011E).

- Note 1: This definition includes adverse events resulting from insufficient or inadequate instructions for use, deployment, implantation, installation, or operation, or any malfunction of the investigational medical device
- Note 2: This definition includes any event resulting from use error or from intentional misuse of the investigational medical device

8.1.4. Serious Adverse Device Effect (SADE)

A serious adverse device effect is an adverse device effect that has resulted in any of the consequences characteristic of an SAE (ISO 14155:2011E).

8.1.5. Unanticipated Serious Adverse Device Effect (USADE)

Per ISO 14155:2011E, an unanticipated serious adverse device effect is a serious adverse device effect which by its nature, incidence, severity or outcome has not been identified in the current version of the risk analysis report.

- Note: Anticipated serious adverse device effect (ASADE) is an effect which by its nature, incidence, severity or outcome has been identified in the risk analysis report

8.1.6. Unanticipated Adverse Device Effect (UADE)

Per 21 CFR 812.3(s), an unanticipated adverse device effect (UADE) is any serious adverse effect on health or safety or any life-threatening problem or death caused by, or associated with, a device, if that effect, problem, or death was not previously identified in nature, severity, or degree of incidence in the investigational plan or application (including a supplementary plan or application) or any other unanticipated serious problem associated with a device that relates to the rights, safety, or welfare of subjects.

8.1.7. Device Deficiency, Device Malfunction, and Use Error

All study device deficiencies shall be documented in the eCRF throughout the clinical investigation and appropriately managed by the Sponsor. If a study device deficiency is detected or suspected that could have led to a SADE, it should be documented on the appropriate eCRF, and the device failure and AE (if applicable) must be reported to the Sponsor within 72 hours upon study site staff awareness. All non-study device malfunctions should be reported via the manufacturer's complaints handling process.

A device deficiency is defined as inadequacy of a medical device with respect to its identity, quality, durability, reliability, safety or performance.

- Note: Device deficiencies include malfunctions, use errors, and inadequate labeling.

Device malfunction is defined as a failure of an investigational medical device to perform in accordance with its intended purpose when used in accordance with the instructions for use or clinical investigation plan.

Use error is defined as the act or omission of an act that results in a different medical device response than intended by the manufacturer or expected by the user.

- Note 1: Use error includes slips, lapses, and mistakes.
- Note 2: An unexpected physiological response of the subject does not in itself constitute a use error

(ISO 14155:2011E)

